7.0 Subject Disposition

The number and percentage of subjects will be summarized for each of the following categories, for overall and by country and region:

- Subjects enrolled into the study.
- Subjects who discontinued venetoclax - overall and for each reported primary reason.
- Subjects who discontinued the study - overall and for each reported primary reason.

The number and percentage of subjects who discontinued venetoclax will be summarized by reason (all reasons) and by primary reason (per eCRF). Similar summaries will be provided for discontinuations from the study.

The number and percentage of subjects with reported venetoclax interruptions will be summarized. Reasons for venetoclax interruptions will be presented in the listings.

8.0 Demographics, Baseline Characteristics, Medical History, and Previous Concomitant Medications

8.1 General Consideration

The safety population will be used to summarize baseline variables. The safety population also will be used to summarize medical history and previous, concomitant, and post-treatment medications.

8.2 Demographic and Baseline Characteristics

Categorical baseline variables will be summarized with the number and percentage of subjects in each category. Continuous baseline variables will be summarized with descriptive statistics (number of non-missing observations, mean, standard deviation, median, maximum and minimum).

Categorical baseline variables include:

- Sex (male, female)
- Race (White, Black or African American, Asian, and Other)
- Geographic region (EUROPE, and ROW)

- Ethnicity (Not Hispanic or Latino, and Hispanic or Latino)
- Age (< 65, ≥ 65, < 75, and ≥ 75)
- Tobacco use (current, former, never, and unknown)
- Alcohol use (current, former, never, and unknown)
- ECOG performance status (grade: 0, 1, 2)
- LDH (≤ ULN, > ULN)
- Prior number of oncology therapies (1, 2, ≥ 3)
- Previous line of Ibrutinib failure (1, > 1)
- Previous line of Idelalisib failure (1, > 1)
- 17p deletion status (deleted, not deleted, indeterminate)
- Rai stage (0, 1, 2, 3, 4)
- Binet stage (A, B, C)
- IgVH status (mutated, unmutated)
- ZAP-70 (positive, negative, indeterminate)
- CD-38 (positive, negative, indeterminate)
- Beta 2-microglobulin (< 3 mg/L, ≥ 3 mg/L)
- TP53 mutation (yes, no, unknown)
- 11q (deleted, not deleted, indeterminate)
- 13q (deleted, not deleted, indeterminate)
- 12q trisomy (present, not present, indeterminate)
- Absolute lymphocyte count (ALC) (< $25 \times 10^9/L$, ≥ $25 \times 10^9/L$; < $100 \times 10^9/L$, ≥ $100 \times 10^9/L$)
- Bulky disease nodes (< 5 cm, 5 cm To 10 cm, ≥ 10 cm)
- Prior BCRi treated (yes, no)
- TLS risk category (low/medium, high)
- Hospitalized for TLS prophylaxis before venetoclax (yes, no)

Continuous baseline variables include:

- Age (year)

- Weight (kg) by male and female
- Height (cm)
- Number of prior oncology therapy
- Beta-2 microglobulin (MG/L)
- Lactate dehydrogenase (LDH)
- Absolute lymphocytes count ($10^9/L$)
- Bulky disease nodes (cm)
- Duration of BCRi therapy before venetoclax

8.3 Medical History

Medical history data will be summarized and presented using body systems and conditions/diagnoses as captured on the CRF. The body systems will be presented in alphabetical order and the conditions/diagnoses will be presented in alphabetical order within each body system. The number and percentage of subjects with a particular condition/diagnosis will be summarized. Subjects reporting more than one condition/diagnosis within a body system will be counted only once for that body system.

8.4 Previous Treatment and Concomitant Medications

A prior medication is defined as any medication taken prior to the first dose of venetoclax. A concomitant medication is defined as any medication that started prior to the first dose of venetoclax and continued to be taken after the first dose of venetoclax or any medication that started after the first dose of venetoclax, but not after the last dose of venetoclax. The number and percentage of subjects who have taken medications will be summarized by generic drug name for prior medications, concomitant medication, and prior oncology therapies. In addition, the number and percentage of subjects who have taken, one, two, three, four, and five or more drugs will be summarized for prior medications, concomitant medications, and prior oncology therapies.

For summaries of concomitant medications, if an incomplete start date was collected for a medication, the medication will be assumed to be a concomitant medication unless there is evidence that confirms that the medication was not a concomitant medication (e.g., the medication end date was prior to the first dose of venetoclax).

A subject who reports the use of two or more medications will be counted only once in the summary of "Any Concomitant Medication." A subject who reports two or more uses of the same medication will be counted only once in the total for the associated generic drug name. Similar rules apply to prior medications as well.

9.0 Venetoclax Exposure and Compliance

The duration of exposure to venetoclax will be summarized. Duration of exposure is defined for each subject as (last dose date – first dose date) + 1. Duration of exposure will be summarized using the following statistics: sample size (N), mean, standard deviation, median, and range. In addition, the number and percentage of subjects exposed to venetoclax will be summarized for the following categories of exposure duration: 0 to 5 weeks, > 5 weeks to 8 weeks, > 8 weeks to 12 weeks, > 12 weeks to 16 weeks, > 16 weeks to 20 weeks, > 20 weeks to 24 weeks, > 24 weeks to 28 weeks, > 28 weeks to 32 weeks, > 32 weeks to 36 weeks, > 36 weeks to 48 weeks, > 48 weeks to 60 weeks, and > 60 weeks.

The compliance based on investigator opinion for each subject will be provided in the listing.

10.0 Quality of Life and Efficacy Analyses

10.1 General Considerations

Details on the analysis sets used will be specified in quality of life and efficacy analyses described below.

10.1.1 Definitions for Quality of Life Assessments

EORTC QLQ-C30

Quality of life and symptoms will be assessed with the European Organization for Research and Treatment of Cancer (EORTC) Quality of Life Questionnaire Core 30 (EORTC-QLQ-C30) version 3¹. The QLQ-C30 is a 30-item subject self-report questionnaire composed of both multi-item and single scales, including five functional scales (physical, role, emotional, social, and cognitive), three symptom scales (fatigue, nausea and vomiting, and pain), a global health status/quality of life (GHS/QoL) scale, and six single items (dyspnea, insomnia, appetite loss, constipation, diarrhea, and financial difficulties). Subjects rate items on a four-point scale, with 1 as "not at all" and 4 as "very much." The EORTC QLQ-C30 was developed and validated for use in a cancer subject population, and its reliability and validity is highly consistent across different language cultural groups. A change of 5 – 10 points is considered a small change, and the lower bound (5) is being used to define the minimum important difference (MID). A change of 10 – 20 points is considered a moderate change.

The EORTC-QLQ-C30 domains (global health status/quality of life, physical, role, emotional, social, cognitive, fatigue, nausea and vomiting, pain, dyspnoea, insomnia, appetite loss, constipation, diarrhea, and financial difficulties) will be summarized (mean, standard deviation, and median) at each assessment. In addition the mean change in each of these values (visit-level assessment versus baseline) will be calculated to identify any statistically significant differences. The ninety-five percent (95%) confidence interval of the mean change will be constructed based on (a) without model assumption and (b) with model assumption. A linear model will be used for the analysis of repeated measures where the covariance pattern will be assumed as compound symmetry (CS).

EORTC QLQ-CLL16

The EORTC QLQ-CLL16 was designed specifically for subjects with stage 0 to stage 4 CLL². It is comprised of sixteen questions that address five domains of HRQoL important in CLL. There are three multi-item scales assessing Fatigue (2 items), Disease

and Treatment Effects (7 items), and Infection (5 items), and two single-item scales assessing Social Activities and Future Health Worries. Subjects rate items on a four-point scale, with 1 as "not at all" and 4 as "very much." A negative change in score from baseline represents an improvement in symptoms. A change of 5 – 10 points is considered a small change, and the lower bound (5) is being used to define the minimum important difference (MID). A change of 10 – 20 points is considered a moderate change.³

The EORTC-QLQ-CLL16 domains (Fatigue, Treatment Side Effects and Disease Symptoms, Infection, Social Activities, Future Health Worries) will be summarized (mean, standard deviation, and median) at each assessment. In addition the mean change in each of these values (visit-level assessment versus baseline) will be calculated to identify any statistically significant differences. The ninety-five percent (95%) confidence interval of the mean change will be constructed based on (a) without model assumption and (b) with model assumption. A linear model will be used for the analysis of repeated measures where the covariance pattern will be assumed as compound symmetry (CS).

EQ-5D-5L

The EuroQol EQ-5D-5L is a generic preference instrument that has been validated in numerous populations⁴⁻⁵. The EQ-5D-5L has five dimensions: mobility, self-care, usual activities, pain/discomfort and anxiety/depression. These dimensions are measured on a five-level scale: no problems, slight problems, moderate problems, severe problems, and extreme problems. The scores for the 5 dimensions are used to compute a single utility index score ranging from zero (0.0) to 1 (1.0) representing the general health status of the individual. The EQ-5D-5L also contains a visual analog scale (VAS) to assess the subject's overall health. The MID for the EQ-5D utility index score in cancer subjects is 0.08, and the MID for EQ-5D VAS is 7⁶.

Each of the five dimensions of the EQ-5D-5L, the VAS and overall utility score will be calculated using the EuroQol scoring manual, and summarized (mean, std. dev., median)

at each assessment. The impact of treatment over time will be assessed by calculating the change in score from baseline at each assessment time point. The ninety-five percent (95%) confidence interval of the mean score change will be constructed based on (a) without model assumption and (b) with model assumption. A linear model will be used for the analysis of repeated measures where the covariance pattern will be assumed as compound symmetry (CS).

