Duration of Treatment:	
Subjects may continue receiving venetoclax for up to 2 years provided they continue to tolerate the drug, have no evidence of disease progression (based on investigator assessment), do not have unacceptable toxicity, and do not meet any of the criteria for subject discontinuation. After treatment discontinuation, subjects will be followed for disease progression (if progression has not already occurred) and survival. Post-treatment calls will be performed every 6 months until discontinuation from the study. Survival information (i.e., the date and cause of death, post-treatment cancer therapies, date of progression etc.) will be collected. This period will continue for 2 years following discontinuation of venetoclax.
 
In countries where venetoclax is not commercially available, subjects who continue to derive benefit after 2 years of treatment, may be able to extend their treatment for up to 2 additional years. AbbVie will work with the investigator on a case by case basis to consider the potential continuation of venetoclax therapy.

Criteria for Evaluation:	
Quality of Life: Quality of life will be assessed based on patient-reported outcome (PRO) measures, including the EORTC QLQ-C30, EORTC QLQ-CLL16, and EQ-5D-5L.
 
Efficacy: Disease response will be assessed by the investigator, based on laboratory results, physical examinations, using the 2008 modified IWCLL NCI-WG Criteria for Tumor Response including CT imaging (or MRI in the case CT is medically contraindicated) and bone marrow biopsy and aspirate for subjects with CR to confirm the response.
 
All measurable disease must be documented at Screening (baseline) by physical examination, laboratory testing, and CT scan (or MRI in the case CT is medically contraindicated). During the study, clinical disease assessments will take place at Week 24, Week 36, and Week 48. To confirm the response, a CT scan will be performed at Week 48.
 
Safety: Adverse event monitoring, vital signs, physical examination, and laboratory assessments will be evaluated.

Statistical Methods:

The study analyses will be descriptive. All subjects participating in the study who received at least one dose of venetoclax will be included in the analyses unless otherwise noted in the separate, statistical analysis plan (SAP).

Study Variables:

Quality of Life:

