6.3 Definition of Analysis Windows

For visit wise analyses including quality of life and safety analyses, the time windows specified in [Table 2](#) and [Table 3](#), describe how the data will be assigned to protocol specified visits. Analysis time windows will be constructed using the following algorithm:

- Determine the nominal study Rx day for each scheduled visit.
- Determine the time window around a specific nominal study Rx day as in [Table 2](#).
- If more than one assessment is included in a time window the most conservative value (i.e., the smallest score) should be used for the analysis of quality of life measures. A sensitivity analysis should be performed based on considering the most favorable (i.e., the largest value) assessment of the quality of life measures. Except the quality of life measures, if there are two observations with equal distance to the nominal day, the latest one will be used in analyses.

Table 2. Time Windows for Quality of Life Measures

Scheduled Visit	Nominal Day	Time Window (study Rx day range)
Baseline (Week 1 Day -1 or Week 1 Day 1)	≤ 1	See the baseline definition (Section 6.0)
Week 4 Day 1	22	2 to 43
Week 8 Day 1	50	44 to 71
Week 12 Day 1	75	72 to 153
Week 24 Day 1	162	154 to 237
Week 36 Day 1	246	238 to 321
Week 48 Day 1	330	322 to 405
Week 60 Day 1	414	406 to 489
Week 72 Day 1	498	490 to 573
Week 84 Day 1	582	574 to 657
Week 96 Day 1	666	658 to 743
Week 108 Day 1	750	742 to 825
Final Observation	Last non-missing value within 30 days of last dose of Venetoclax	

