10.2.2 Secondary Efficacy Analyses

ORR and CR will be assessed as the proportion of subjects with an overall response based on the IWCLL NCI-WG criteria. The 95% confidence interval based on the Clopper-Pearson exact method for binomial distribution will be constructed for the calculated ORR and CR rates.

DOR, TTP, PFS, and OS will be analyzed by Kaplan-Meier methodology using data for all subjects defined in Section 5.1.1. Median time of each endpoint will be calculated and 95% confidence interval for median time of each endpoint will be presented.

Secondary quality of life endpoints will include all multi-item scales and single-item scales from the EORTC QLQ-C30, EORTC QLQ-CLL16, and EQ-5D-5L. Scores will be calculated based on the scoring manual for each instrument. The mean change score from baseline to post-baseline (Week 4, Week 12, Week 24, Week 36, Week 48, Week 60, Week 72, Week 84, Week 96, and Week 108/Final visit) will be summarized with the 95% confidence interval. Mean score with SD of baseline and each post-baseline visit also will be presented.

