10.4 Handling of Multiplicity

There will be no multiplicity adjustments performed in this open arm study.

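### SAP 10.1.1 sets an unadjusted, unlabelled search for significance over 20 QoL domains at every visit, which conflicts with the protocol's statement that analyses are descriptive

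*SAP*

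**What the plan says.** SAP 10.1.1 describes the QLQ-C30 as having "five functional scales (physical, role, emotional, social, and cognitive), three symptom scales (fatigue, nausea and vomiting, and pain), a global health status/quality of life" scale and six single items, which is 15 domains. After listing the summaries for each domain it adds: "In addition the mean change in each of these values (visit-level assessment versus baseline) will be calculated to identify any statistically significant differences". The same sentence is repeated for the QLQ-CLL16, whose five domains are given as: "The EORTC-QLQ-CLL16 domains (Fatigue, Treatment Side Effects and Disease Symptoms, Infection, Social Activities, Future Health Worries) will be summarized". In both cases it continues: "The ninety-five percent (95%) confidence interval of the mean change will be constructed based on (a) without model assumption and (b) with model assumption". No alpha, p-value or named test is given for these comparisons.

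SAP 10.4 states: "There will be no multiplicity adjustments performed in this open arm study". SAP 10.2.2 calls the non-primary scales secondary and plans means, SDs and 95% confidence intervals for them. It gives them no descriptive, exploratory or nominal label.

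Two other texts point the other way. The Statistical Methods part of the protocol synopsis says: "The study analyses will be descriptive". The EQ-5D-5L paragraphs of SAP 10.1.1 plan change scores and the same two kinds of interval, but say nothing about finding significant differences.

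The primary endpoint is fixed in SAP 10.2.1 and Protocol 8.1.2.1 as the GHS/QoL change from baseline to Week 48. Its one-sided alpha of 0.025 appears only in the sample size sections (SAP 4.3, Protocol 8.2 and synopsis).

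**The concern.** The sentence in SAP 10.1.1 gives the domain-by-visit grid a purpose, which is to find significant changes. It supplies neither error control nor a statement that the findings are nominal. These are the only places where the SAP speaks of statistical significance for quality of life. The primary analysis in SAP 10.2.1 is written purely as means, SDs and intervals. So the explicit significance search covers the whole grid and does not single out the one comparison that the trial was sized for.

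Quality of life is the trial's primary objective, and the trial is single-arm and open-label. A programmer following the SAP literally would flag every domain and visit whose interval excludes zero. A report writer would then have grounds in the SAP to describe those cells as statistically significant, although the protocol calls the analyses descriptive.

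**Working it through.** **The plan's own figure.** The documents give no error rate for the grid. The nearest stated figure is the 177 subjects for the primary. With SD 20.5, a change of 5, one-sided 0.025 and 90% power, n = (20.5 × (1.9600 + 1.2816) / 5)² = 176.6, rounded up to 177. This reproduces. It describes one test of zero mean change in GHS/QoL at Week 48 and says nothing about the other comparisons.

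**Counting the comparisons.**
- Domains: 15 + 5 = 20 (SAP 10.1.1).
- Post-baseline visits: 11 in SAP Table 2, which includes the row "Week 8 Day 1 50 44 to 71". SAP 10.2.1 and 10.2.2 list 10, omitting Week 8: "Week 4, Week 12, Week 24, Week 36, Week 48, Week 60, Week 72, Week 84, Week 96, and Week 108/Final visit".
- 20 × 11 = 220, less the primary = 219. With the 10-visit list, 20 × 10 − 1 = 199.
- At Week 48 alone, 20 − 1 = 19 domains other than GHS/QoL.

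EQ-5D-5L is left out because its text does not carry the significance clause.

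**Assumptions.** The two-sided 5% level is inferred from the unadjusted 95% intervals. No domain truly changes at any visit. The documents give no correlations, so a common correlation ρ from 0.3 to 0.8 is assumed between all comparisons.

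**Formula.** With c = 1.96 and m comparisons, the chance of at least one false positive in either direction is

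1 − ∫ [Φ((c − √ρ·t)/√(1−ρ)) − Φ((−c − √ρ·t)/√(1−ρ))]^m φ(t) dt.

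For false improvement only, drop the second Φ term.

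| Comparisons | Direction | ρ = 0.3 | ρ = 0.5 | ρ = 0.8 |
|---|---|---|---|---|
| 219 (11 visits) | either | 0.996 | 0.92 | 0.43 |
| 219 (11 visits) | improvement | 0.71 | 0.50 | 0.22 |
| 199 (10 visits) | either | 0.99 | 0.90 | 0.42 |
| 199 (10 visits) | improvement | 0.70 | 0.49 | 0.21 |
| 19 (Week 48 only) | either | 0.53 | 0.41 | 0.22 |
| 19 (Week 48 only) | improvement | 0.27 | 0.205 | 0.11 |

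Whatever the correlation, the expected number of false positives among the 219 is 219 × 0.05 = 10.95, about half of them improvements.

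**Sensitivity to the correlation model.** A simulation with separate correlations between domains (0.3 to 0.7) and between visits (0.5 to 0.7), over all 20 domains and 11 visits, gave 0.82 to 0.996 in either direction and 0.44 to 0.81 for false improvement.

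**Not counted.** Each comparison gets two intervals, one with and one without a model, and no rule says which decides significance. This would raise the figures somewhat.

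**The case against.** The strongest reply is that this is loose drafting with little consequence. The clause sits in a definitions section. The analysis sections (SAP 10.2.1, 10.2.2) plan only summaries and intervals and do not mention significance, and the EQ-5D-5L text omits the clause. The lack of adjustment is openly declared in SAP 10.4. The protocol, which the SAP says it elaborates, calls the analyses descriptive. Unadjusted intervals for secondary patient-reported outcomes in a single-arm Phase 3b study are not in themselves an error. The no-change scenario is also pessimistic, since Protocol 3.2 cites substantial QoL improvement in the earlier 17p deletion study.

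A further argument is that SAP 10.1.1 gives a clinical yardstick, a 5-point minimum important difference. If SD 20.5 and n = 177 applied to every scale and visit (an assumption), the standard error would be 20.5/√177 = 1.54. Nominal significance would then need about 1.96 × 1.54 = 3.0 points. The chance that any of 219 null comparisons reached 5 points in either direction would be about 0.09 at ρ = 0.5 (0.15 at 0.3, 0.03 at 0.8).

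Much of this stands. It limits the point to a conflict in wording with a measurable consequence. It does not remove the conflict: the SAP is the document that guides programming, it states the significance purpose twice, and it does not make the 5-point threshold a condition for calling a change significant.

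A reader might infer that a missed Week 48 primary could be rescued by a significant GHS/QoL result at another visit or by another domain. The documents do not support that. The primary is one scale at one visit with its own one-sided 0.025, and no passage lets another result stand in for it.

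**Conclusion.** The point holds as an inconsistency between the SAP and the protocol, and within the SAP, that permits uncontrolled significance statements on non-primary quality-of-life results. Under no true change, at least one spurious significant result among the 219 comparisons has probability 0.43 to 0.996, or 0.22 to 0.71 for false improvement. At Week 48 alone the ranges are 0.22 to 0.53 and 0.11 to 0.27. The choice between 10 and 11 visits hardly matters. These figures rest on an inferred 5% level, assumed correlations and the absence of any true change.

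A reader might go further and conclude that false quality-of-life claims are very likely, or that the report is bound to contain one. The documents do not support that. The lower ends of the ranges are well below one half, some domains may truly change, and no rule converts a significant domain into a claim of success. The error rate of the primary test is unaffected.

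**What to change.** In SAP 10.1.1, end the sentence "In addition the mean change in each of these values (visit-level assessment versus baseline) will be calculated to identify any statistically significant differences" after the word calculated, in both the QLQ-C30 and the QLQ-CLL16 text. This brings them into line with the EQ-5D-5L text.

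In SAP 10.4, add that the only inferential comparison is the GHS/QoL change from baseline to Week 48, at the one-sided 0.025 of the sample size section. State that all other domains, instruments and visits, including GHS/QoL at other visits, are descriptive, and that their 95% confidence intervals are nominal and will not be described as statistically significant.

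Reword the synopsis sentence on descriptive analyses so that it allows for this single inferential comparison. While editing, reconcile the visit lists in SAP 10.2.1 and 10.2.2 with Table 2 on Week 8.

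The sponsor gives up unadjusted significance statements on secondary domains and other visits. Sample size, data collection and the planned summaries do not change. A formal multiplicity procedure for the secondary domains is not needed to resolve this point.

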4.5 Timing of Quality of life and Efficacy Analyses and Safety Evaluations

Table 1. Summary of Analyses with Cutoff Dates and Data Included

Reason	Database Version	Cutoff Date	QoL/Efficacy Data Included	Safety Data Included
DMC	A	24 Apr 2017	Not included	All safety data ^a
DMC	F	03 Nov 2017	Not included	All safety data ^a
DMC	G	30 Apr 2018	Included	All safety data ^a

a. Safety population is defined in Section 5.1.1.

Quality of life, efficacy, and safety analysis occur when all subjects participating in the study have completed the 48-week disease assessment or have discontinued venetoclax (including early termination of the study). Quality of life, efficacy, and safety data up to the cutoff date specified in Table 1 will be considered. During this data collection period, active subjects continue to receive venetoclax, as applicable. When data collection is complete and all data management quality assurance (QA) and quality control (QC) procedures are performed, the clinical database data should be extracted for documentation and statistical analyses. The study will be considered completed when the last enrolled subject discontinues or completes the dosing regimen.

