6.2 Treatment Days

Definition of Treatment Days (Days Relative to the First Dose of Venetoclax)

Treatment (Rx) days are calculated for each time point relative to the first dose date of venetoclax. They are defined as the number of days between the day of the first dose of venetoclax and the specific time point. Rx days are negative values when the time point of interest is prior to the first venetoclax dose day. Rx days are positive values when the time point of interest is after the first venetoclax dose day. The day of the first dose of

venetoclax is defined as Rx Day 1, while the day prior to the first venetoclax dose is defined as Rx Day –1 (there is no Rx Day 0).

Definition of Final Observation

The final observation (Final Visit) is defined as the last non-missing observation collected within 30 days following the last dose of venetoclax, unless otherwise specified.

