6.4 Missing Data Imputation

Subjects with missing disease progression date, missing death date, or missing last known alive date will be considered as censored subjects for time to progression, progression free survival analysis, and survival analysis. And the subject will be censored at the interim data cutoff date.

If a respondent answers at least 50% of the items in quality of life measures, the missing items will be imputed with the average score of the answered items in the same scale. In cases where the respondent did not answer at least 50% of the items, the score for that domain will be considered missing.

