10.2.1 Primary Endpoint Analysis

The primary endpoint will be assessed by the GHS/QoL subscale of the EORTC QLQ-C30. Summary stats will be on mean change. The endpoint (at subject level) will be mean change from baseline to Week 48. Scores will be calculated based on the scoring manual. Mean score for baseline visit and post-baseline visit (Week 4, Week 12, Week 24, Week 36, Week 48, Week 60, Week 72, Week 84, Week 96, and Week 108/Final visit) will be reported with standard deviation (SD). The 95% confidence interval for mean change additionally will be provided for each post-baseline versus baseline.

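### The Week 48 GHS/QoL change has no planned drop-out sensitivity analysis, and its one model-based interval fixes compound symmetry, which can make that interval too narrow

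*SAP*

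**What the plan says.** SAP 10.2.1 defines the primary endpoint: "The endpoint (at subject level) will be mean change from baseline to Week 48". It then adds: "The 95% confidence interval for mean change additionally will be provided for each post-baseline versus baseline". It mentions no model and gives no rule for a subject without a Week 48 score.

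SAP 10.1.1 says that the interval for each QLQ-C30 domain, GHS/QoL included, will be "constructed based on (a) without model assumption and (b) with model assumption", and specifies the model in one sentence: "A linear model will be used for the analysis of repeated measures where the covariance pattern will be assumed as compound symmetry (CS"). It does not state the visits fitted, the response (score or change), the fixed effects or the type of standard error, and does not say which interval is primary.

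The other places where a drop-out rule could stand are these:

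- **SAP 5.1.1 and 4.3.** The analysis population is all dosed subjects, and 200 are to be dosed to allow for drop-outs.
- **SAP 6.4.** Imputation is at item level only. If fewer than half the items are answered, "the score for that domain will be considered missing".
- **SAP 6.3.** "A sensitivity analysis should be performed based on considering the most favorable (i.e., the largest value) assessment of the quality of life measures". This concerns several scores in one window, not absent ones.
- **SAP 6.2.** "The final observation (Final Visit) is defined as the last non-missing observation collected within 30 days following the last dose of venetoclax". This summary can hold early stoppers' last scores, but it mixes scores from different weeks.
- **SAP 4.5.** The "analysis occur when all subjects participating in the study have completed the 48-week disease assessment or have discontinued venetoclax".

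**The concern.** Questionnaires are collected until the end of treatment, with a Final Visit soon after stopping (Protocol 5.3.1.1 and 5.4.1). A Final Visit score counts at Week 48 only if it falls on treatment days 322 to 405 (SAP Table 2), so a subject who stops early will usually have no Week 48 score.

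The protocol synopsis calls the analyses descriptive, which makes the Week 48 mean change and its 95% interval the primary result. SAP 10.1.1 also intends to read the changes for statistical significance. As planned, one interval may not describe all dosed subjects, the other rests on a covariance pattern that the SAP neither justifies nor relaxes, and no analysis shows how much drop-out matters.

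Compound symmetry (CS) gives every pair of visits the same correlation. If correlation in fact decays with time, the fitted value is an average over mostly closer pairs. When Week 48 is the last visit fitted, baseline and Week 48 are the most distant pair, so the average is too high for them and the variance of their difference is understated.

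**Working it through.** **Inputs from SAP 4.3.** Difference 5, SD 20.5, one-sided alpha 0.025, power 90%, 177 evaluable, 200 dosed. The one-sample normal formula gives (20.5 × (1.960 + 1.282) / 5)² = 176.6, so 177 is reproduced. The implied missing fraction is 1 − 177/200 = 11.5%.

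**Assumptions.** The documents give no correlations, drop-out mechanism or entry span, and no gap between subjects with and without a Week 48 score. Point half-widths take 20.5 as the SD of the change; SAP 4.3 ties it only to the subscale.

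**Interval (a): selection.** Shift = fraction missing × gap. At 11.5% and a gap of 5 to 15 points: 0.115 × 5 = 0.6 to 0.115 × 15 = 1.7 points. Simulations with true change 5.0 (1,500 trials per setting) gave:

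| Drop-out follows | Missing | Observed-case mean | Coverage |
|---|---|---|---|
| falling score | 11.5% | 6.0–6.1 | 89–91% |
| falling score | 20% | 6.7–7.0 | 77–82% |
| low score level | 11.5% | 4.75–4.97 | about 95% |
| low score level | 20% | 4.57–4.97 | about 95% |

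The sign of the shift changes with the mechanism.

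**Interval (b): closed form, complete data, equal variances.** Let ρ(w) be the correlation at a lag of w weeks, ρ48 its value at 48 weeks, and ρ̄ its mean over all pairs of fitted visits.

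- Score model: CS SE / true SE = √[(1 − ρ̄)/(1 − ρ48)].
- Change-score model: the same, with ρ̄ replaced by the mean of ρ between baseline and each later visit.
- Coverage = 2Φ(1.96 × ratio) − 1.

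Score model, visits 0, 4, 8, 12, 24, 36 and 48:

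| Assumed ρ(w) | ρ48 | ρ̄ | Ratio | Coverage |
|---|---|---|---|---|
| flat 0.5 (CS holds) | 0.5000 | 0.5000 | 1.000 | 95.0% |
| mild: 0.5 + 0.1·exp(−w/20) | 0.5091 | 0.5420 | 0.966 | 94.2% |
| mild: 0.6·exp(−w/300) | 0.5113 | 0.5594 | 0.950 | 93.7% |
| mild: 0.6·exp(−w/200) | 0.4720 | 0.5405 | 0.933 | 93.3% |
| moderate: 0.7·exp(−w/100) | 0.4331 | 0.5706 | 0.870 | 91.2% |
| moderate: 0.7·exp(−w/60) | 0.3145 | 0.5027 | 0.852 | 90.5% |
| moderate: 0.75·0.99^w | 0.4630 | 0.6107 | 0.851 | 90.5% |
| steep: 0.3^(w/48) | 0.3000 | 0.6181 | 0.739 | 85.2% |
| steep: 0.5^(w/48) | 0.5000 | 0.7485 | 0.709 | 83.5% |

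For example, √[(1 − 0.6107)/(1 − 0.4630)] = 0.851. SAP 10.2.1 omits Week 8 from its visit list. With or without Week 8, and for either model, the moderate patterns give 0.85–0.89 (coverage 90.5–91.8%) and all decaying patterns about 0.71–0.97.

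Random drop-out adds to the shortfall. For 0.5^(w/48) with 11.5% missing, the CS SE is 1.06 against a true 1.52, and coverage is 82.9%.

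**Visits after Week 48.** At the analysis time in SAP 4.5 the last enrolled subjects have no later visits. Simulated with uniform entry over 26 to 60 weeks and no drop-out, the moderate patterns give 0.87–0.93 (coverage 91.3–93.0%). With complete data to Week 108, the closed form over all decaying patterns gives about 0.92–1.01.

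**Unstructured alternative.** With baseline in the response vector and the drop-out mechanisms above, the mean estimate was 4.97–4.99 and coverage 94.9–95.9% in every setting. Half-widths at 11.5% missing were 2.96 for this model, 2.51–2.57 for CS under moderate decay, 2.96 for CS where CS holds, and 3.00–3.04 for the observed-case interval.

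**Delta analysis.** A delta of 5 to 10 points at 11.5% missing moves the mean by 0.115 × 5 = 0.6 to 0.115 × 10 = 1.2 points.

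**The case against.** The strongest case is that CS may never touch the primary result. SAP 10.2.1 mentions no model, so the model-free interval is at least as natural a reading of the primary analysis, and it needs no covariance assumption. That stands as a reading, but the SAP does not settle it, and that interval leaves out subjects without a Week 48 score. It is also fair that the SAP never says the model uses drop-outs' earlier scores; this follows from its being a repeated-measures model.

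A reader might infer that CS always makes the interval too narrow once correlation decays. The documents do not support this, because the direction also depends on the visits fitted, which SAP 10.1.1 does not state. The visits listed in SAP 10.2.1 run to Week 108, and with complete data that far the ratio reaches 1.00 or slightly more in some cases.

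A reader might also take 0.85–0.89 as the size of the effect. It belongs to three assumed patterns that resemble one another; milder and steeper decay widen it to 0.71–0.97.

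Finally, a reader might infer that the observed-case mean is biased upwards. That holds in the simulation where drop-out follows falling scores, but not where it follows a low score level, and nothing in the documents favours either.

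**Conclusion.** The gap is certain from the text: no planned analysis addresses subjects without a Week 48 score, and no primary Week 48 interval is named. The covariance point is conditional. It needs model-based standard errors, similar variances across visits, correlation that decays with time, and Week 48 as the last visit fitted. The SE ratio is then about 0.71–0.97, and the shortfall shrinks or vanishes as later visits are added. If CS holds, the model interval is correct.

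The size rests wholly on assumed correlations, and the half-widths also on 20.5 being the SD of the change. If 20.5 is instead the SD of the score, the SD of the change is 20.5 × √[2(1 − ρ48)] = 21.2 to 24.0 under the moderate patterns, and the half-width for 177 subjects is 1.96 × SD/√177 = 3.1 to 3.5 rather than 3.0. The sample size of 177 is not in question. The change should be made; confidence is medium.

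**What to change.** In SAP 10.1.1 and 10.2.1:

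1. Name the primary Week 48 estimate.
2. For the model interval, replace CS with unstructured covariance: repeated GHS/QoL scores with baseline in the response vector, visit as the only fixed effect, visits to Week 48, and the Week 48 minus baseline contrast with its 95% interval. Do not substitute change adjusted for baseline with a model-based SE: in a single arm it leaves out baseline sampling variation (complete-data ratio √[(1 + ρ48)/2] = 0.81–0.87 for the flat and moderate patterns).
3. If the model does not converge, use CS with a robust sandwich SE (simulated coverage 94.1–95.7%, with the same small point shift as CS, about 0.2 points at 11.5% missing under decay). Heterogeneous Toeplitz is a second option, checked here only with complete data.
4. Keep the observed-case mean and the model-free interval as supportive.
5. Add one delta or tipping-point analysis for living subjects with no Week 48 score.
6. State that the likelihood model implicitly projects scores for subjects who died before Week 48, report the number of such deaths, and repeat the model estimate without those subjects.

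The cost is SAP wording and a little programming, with no new data. Where correlation decays, the model interval widens: half-width 2.96 instead of 2.51–2.57 points under the moderate patterns at 11.5% missing. Where CS holds, it is unchanged at 2.96.
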